13.7 Grading of Adverse Event Severity

To report AEs on the eCRFs, the Investigator will use the severity grading as described in NCI CTCAE, v4.03.

Every effort should be made by the Investigator to assess the AE according to CTCAE criteria. If the Investigator is unable to assess severity because the term is not described in NCI CTCAE, Version 4.03, severity of MILD, MODERATE, SEVERE, LIFE-THREATENING, or DEATH may be used to describe the maximum intensity of the AE. For purposes of consistency, these intensity grades are defined as follows:

- Mild (Grade 1): does not interfere with patient’s usual function
- Moderate (Grade 2): interferes to some extent with patient’s usual function
- Severe (Grade 3): interferes significantly with patient’s usual function
- Life-threatening (Grade 4): results in immediate risk of patient’s death

- Death (Grade 5): results in patient's death

Note the distinction between the severity and the seriousness of an AE. A severe event is not necessarily a serious event. For example, a headache may be severe (interferes significantly with patient's usual function) but would not be classified as serious unless it met one of the criteria for serious events.

It is requested that when reporting AEs for which potentially redundant CTCAE terms exist, investigators utilize the more clinically-oriented terminology (for example, "anemia" is preferable to "hemoglobin decreased").

It is also requested that in the setting of a hypersensitivity reaction or suspected hypersensitivity reaction considered by the Investigator to be related to investigational therapy, that investigators report both the specific symptoms associated with the reaction (i.e., "urticaria," "chills," "dyspnea") and also report the appropriate term indicating the hypersensitivity reaction ("allergic reaction," or "infusion-related reaction" or "anaphylaxis" if appropriate [General Disorders and Immune System Disorders; CTCAE v4.03]).

14 Statistical Analysis

14.1 General Considerations

Analyses will be performed on all patients that received any quantity of tagraxofusp (i.e., all treated patients). The baseline value for a given variable is defined as the last measurement for the variable prior to the first infusion of tagraxofusp. Cycle 1 Day 1 for each individual patient is defined as the date the patient receives their first infusion of tagraxofusp.

14.2 Determination of Sample Size

14.2.1 Stage 2 (Patients with CMML Previously Enrolled and Patients with MF)

An objective of Stage 2 is a preliminary assessment of response rates associated with tagraxofusp in CMML and MF. Because available anti-cancer agents are associated with very limited responses in the MPNs evaluated in this study, it is anticipated that an agent that confers a response rate $\geq 10\%$ may be considered active and worthy of additional investigation.

Initially, a sample size of 18 patients with a particular MPN was planned for enrollment in Stage 2. Furthermore, it was planned that in settings where there is evidence that a sufficient proportion of patients have experienced improvement in components of the response criteria, that additional investigation of tagraxofusp in a given MPN may have been considered appropriate based on preliminary data.

Preliminary evidence of activity has been observed in patients with relapsed and/or refractory CMML and MF.

As of July 2021, 36 patients have been enrolled, comprising 20 patients with CMML-1 and 16 with CMML-2; median age was 69 years (range 42–81), and 75% of patients were male. Twenty-three patients (64%) had either high- or intermediate-risk genetics based on CPSS,

GFM, MMM, or ELN risk stratification systems. Prior therapies included HMA in 16 patients (43%), allogeneic stem cell transplantation (allo-SCT) in 3 (8%), and other in 12 (32%); 7 patients (19%) were high-risk and treatment naive. Overall, 16 patients (44%) had baseline palpable splenomegaly; in 12 of these patients, spleen size was ≥ 5 cm below left costal margin. Overall, 4 of 36 (11%) patients achieved bone marrow morphological complete responses (BMCRs), 1 of whom was bridged to allo-SCT; all 4 patients had splenomegaly at baseline. It is noteworthy that 2 of the 4 BMCRs, were observed in patients with high-risk genetic features. Fifteen patients (42%) with baseline splenomegaly had spleen responses; 9 patients (60%) had a $\geq 50\%$ reduction in spleen size, including 5 (42%) with splenomegaly of ≥ 5 cm at baseline.

[figure not shown]
14.2.2 Stage 3A in Patients with CMML

The purpose of Stage 3A is to evaluate the clinical benefit derived from individual components, or variations thereof, of the MDS/MPN 2015 criteria that may allow for a prospective definition of a primary efficacy endpoint, that will provide the primary evidence of efficacy for regulatory decision-making in the planned confirmatory cohort (Stage 3B; to be added under the auspices of separate amendment). Individual evaluations will be performed for each of the two CMML cohorts in Stage 3A.

Approximately 20 patients with CMML may be enrolled in each of the two cohorts in Stage 3A to ensure a sufficient number of patients with specific baseline disease characteristics are enrolled to reject a meaningless rate of clinical activity in subsets of interest. (For our purposes, a meaningless rate will be taken to mean that there are no responders, using the definitions below, in the sample for each of the following subsets.) No formal stratification will be performed; however approximately 8-10 patients with baseline splenomegaly (defined as ≥ 5 cm below the left costal margin) and approximately 8-10 patients who are transfusion-dependent at baseline (receipt of at least 4 transfusions within 8 weeks before the first tagraxofusp dose) will be included in each 20-patient cohort. This intended enrollment distribution may be adjusted, depending on the actual prevalence of splenomegaly and transfusion-dependence seen in the general patient population as the study continues to enroll.

In this exploratory stage, the primary evidence of activity in each subset would be (1) a reduction in spleen volume that correlates with an improvement in symptom score or (2) conversion from transfusion-dependent to transfusion-independent. These occurrences on a per-patient basis would be considered responses within each subgroup. Clinical activity would have been demonstrated if at least 1 patient achieves either of these clinically important outcome responses. Up to 5 additional patients with either of these specific baseline characteristics may be enrolled in Stage 3A, to increase the confidence in the observed results, if necessary. It can be seen in the graph below that for any true rate of response that is ≥ 0.15 , this approach would have at least 80% power to detect at least one responder. Given at least a single responder, additional methods such as confidence interval estimation or formal power calculations, may be used to determine whether to move ahead with a confirmatory Stage 3B.

The operating characteristics of this approach to sample size estimation in Stage 3A may be seen in the following graph. This graph presents the sample size required to have either an 80%, 90%, or 95% probability of at least 1 responder when the sample size is N, and the true probability of response is P.

As an example, if the true response probability were 0.15, 10 patients evaluated for a given response type would result in at least one response with 80% probability.

Other subsets of patients may be retrospectively identified in which treatment with tagraxofusp may result in clinically important outcomes, and enrichment strategies within the framework of this sample size may be applied, with the same objective of rejecting a meaningless rate of clinical activity.

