2. PATIENT POPULATION

2.1. Population Definitions

The following patient populations will be evaluated and used for presentation and analysis of the data for all trial stages:

- Modified Intent-to-Treat (mITT) Population: All patients who are eligible based on the screening criteria who received at least 1 dose of tagraxofusp and are evaluable for efficacy (has an efficacy assessment after first treatment or discontinued due to death or progressive disease) prior to that time. Patients will be grouped according to the planned dose level at time of enrollment.
- Per-Protocol (PP) Population: All patients from the mITT population who are compliant with all major aspects of the protocol and have received at least 1 cycle of tagraxofusp (or treatment was delayed or patient discontinued treatment early due to safety finding related to study treatment). Patients will be grouped according to the planned dose level at time of enrollment.
- Immunogenicity Population: All patients enrolled in the study who received at least 1 dose of tagraxofusp and had at least 1 non-missing immunogenicity sample result.
- PK Population: All subjects who receive at least 1 dose of Tagraxofusp, have at least one plasma sample collected, and the corresponding plasma PK concentration is quantifiable.
- Safety Population: All patients enrolled in the study who received at least 1 dose of tagraxofusp. Patients will be grouped according to the actual dose level received.

The mITT population is the primary population for the analysis of efficacy parameters, and will be used to support baseline endpoints. The immunogenicity population will be used for summary of immunogenicity results. The PK population will be used for the analysis and summary of PK data. The Safety population is the primary population for the analysis of disposition, baseline, and safety endpoints. Patients included in the PP population or reasons for exclusion from the PP population will be identified in a data listing. Note that the intent-to-treat population, defined as all eligible patients, will not be used in any analyses.

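### Stage 3A claims at least 80% power for any true response rate of 0.15 or more, but the planned 8-10 patients per subset give 73%, 77% or 80%, and nothing in the plan secures 10

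*Protocol*

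**What the plan says.** The Stage 3A sample size is justified in Protocol 14.2.2 and, in almost the same words, in SAP 3.1.2. A meaningless rate of activity means no responders in a subset, and one responder is enough to show activity.

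- **Subset size.** "No formal stratification will be performed; however approximately 8-10 patients with baseline splenomegaly", and about 8-10 who are transfusion-dependent, are to be included in each cohort of 20.
- **Level of evaluation.** The protocol adds: "Individual evaluations will be performed for each of the two CMML cohorts in Stage 3A".
- **Flexibility.** "This intended enrollment distribution may be adjusted, depending on the actual prevalence of splenomegaly" and of transfusion dependence.
- **Extension.** "Up to 5 additional patients with either of these specific baseline characteristics may be enrolled in Stage 3A", with the purpose "to increase the confidence in the observed results, if necessary".
- **Power.** For any true rate of 0.15 or above, "this approach would have at least 80% power to detect at least one responder". The worked example is that, at 0.15, "10 patients evaluated for a given response type would result in at least one response with 80% probability".

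SAP 2.1 makes the mITT population primary for efficacy. It admits eligible, treated patients who "are evaluable for efficacy (has an efficacy assessment after first treatment or discontinued due to death or progressive disease"). SAP 3.9 says withdrawn patients are not replaced, whereas Protocol 7.2 lets the sponsor add patients at its discretion.

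**The concern.** The power sentence covers the approach as a whole, but the example behind it uses only the largest subset size in the planned range. If 10 is also the smallest number that reaches 80% at a rate of 0.15, the sentence is false for 8 and 9, both of which the plan accepts.

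What is at stake is how often real activity would be missed. Zero responders is the plan's own marker of a meaningless rate, so the probability of seeing none at a true rate of 0.15 is the miss rate of the rule. A reader of the SAP or the study report would take it to be at most 20%.

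**Working it through.** **Inputs.** All come from Protocol 14.2.2 and SAP 3.1.2: true rate p = 0.15; success is at least 1 responder; N = 8 to 10 per subset per cohort. No significance level enters the figure, and SAP 3.7 applies no Type I error control.

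**1. The plan's own figure.** P(at least 1 responder) = 1 − (1 − p)^N. With N = 10, 1 − 0.85^10 = 0.8031, so the stated 80% is reproduced.

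**2. Smallest N for 80%.** ln(0.20)/ln(0.85) = 9.90, so 10 patients are needed.

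**3. The planned range, without the extension.** The last column is 1 − 0.2^(1/N).

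| N | P(at least 1) at 0.15 | Shortfall from 80% | P(none) = 0.85^N | True rate giving 80% |
|---|---|---|---|---|
| 8 | 72.8% | 7.2 points | 27.2% | 0.182 |
| 9 | 76.8% | 3.2 points | 23.2% | 0.164 |
| 10 | 80.3% | none | 19.7% | 0.149 |

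**4. What the extension can do.** Two subsets in two cohorts make four groups. I read the 5 extra patients as the total for Stage 3A.

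- All 5 in one group of 8 gives N = 13 and 1 − 0.85^13 = 87.9%.
- Raising all four groups from 8 to 10 takes 4 × 2 = 8 added memberships. Five patients with one characteristic each supply 5, for example 10/10/9/8, giving 80.3%, 80.3%, 76.8% and 72.8%.
- Four patients with both characteristics, two per cohort, supply 8 and bring all four groups to 10.
- From four groups of 9, four single-characteristic patients are enough.

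If the 5 applies per characteristic or per cohort, more patients are available, but they remain optional.

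**5. Evaluability.** One non-evaluable patient in a group of 10 leaves 9 in the mITT analysis, and the figure falls to 76.8%.

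**The case against.** The strongest reply is that the power sentence directly follows the extension, so the approach should be read to include it. Two extra patients restore 80.3% in a group of 8. The extra patients could also be directed, after results are seen, only to groups with no responder.

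Take four independent groups of 8, with 5 single-characteristic patients split as evenly as possible among the groups with no responder. A given group has none with probability 0.2725. The number of other groups also at zero is then 0, 1, 2 or 3, with probabilities 0.385, 0.433, 0.162 and 0.020. The average chance that the added patients yield a responder in the given group is 0.556, 0.332, 0.235 and 0.182 respectively. The weighted mean is 0.3995, and 0.7275 + 0.2725 × 0.3995 = 83.6%. The arithmetic is sound, but the documents contain no such allocation rule. They leave the extension optional and do not tie it to reaching 10. What stands is that using the extension could restore 80%; the plan does not commit to using it.

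A second reply pools the subsets, since activity is shown if either outcome occurs. Two non-overlapping, independent subsets of 8 give 1 − 0.85^16 = 92.6%. This does not fit a criterion set for each subset, a separate evaluation of each cohort, or an example framed around one response type.

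Three lesser points have some force:

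- The example already shows that 10 patients are needed. It does not say that 8 and 9 fall short.
- Protocol 14.1 analyses all treated patients. On that basis an unassessed patient may count as a non-responder and N stays at 10, so step 5 applies only to the SAP's primary population.
- No decision now rests on the figure. That limits the importance of the error but does not make the sentence right.

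**Conclusion.** The concern holds. Without the optional extension, the stated power of at least 80% at a true rate of 0.15 is met only with 10 patients in a subset. It falls to 76.8% with 9 and 72.8% with 8, and the plan does not secure 10.

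The percentages follow directly from the binomial formula and assume only that the rule is applied per subset and per cohort, as the text indicates. The allocation scenarios also assume that the 5 extra patients are a Stage 3A total. I have not seen the graph that accompanies the text, but its values at 0.15 should follow from the same formula.

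The point is minor. Stage 3A is exploratory, and SAP Section 5 says that its enrolment was not continued, that Stage 3B will not start and that only descriptive analyses remain. The effect is confined to how the design is described in the SAP and the study report.

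**What to change.** Replace the power sentence in Protocol 14.2.2 and SAP 3.1.2 with:

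> 8, 9 or 10 evaluable patients per subset give a 73%, 77% or 80% probability of at least one responder at a true rate of 0.15; at least 80% requires at least 10 evaluable patients, which the optional additional patients may provide.

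If the protocol will not be amended again, make the change in the SAP and carry the same wording into the study report. In either case, report the number of evaluable patients actually reached in each subset of each cohort.

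The cost is one sentence per document and a count in the report. The downside is that the design is then described as giving 73-80% instead of at least 80%.

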3.8. Subpopulations

Exploratory subgroup analyses may be performed for descriptive purposes.

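### Protocol 14.2.2 lets subsets found in retrospect be used to reject a no-responder result, and does not rule out counting the responder who prompted the choice

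*Protocol*

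**What the plan says.** Protocol 14.2.2 sizes Stage 3A around two subsets fixed by baseline features, splenomegaly and transfusion dependence, with about 8-10 patients of each kind in each cohort of about 20. For these, "a meaningless rate will be taken to mean that there are no responders"; the definition refers to the subset's sample and is tied to the two subsets that the text then names. The pass rule is one responder: "Clinical activity would have been demonstrated if at least 1 patient achieves either of these clinically important outcome responses".

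The last paragraph of the section goes further: "Other subsets of patients may be retrospectively identified in which treatment with tagraxofusp may result in clinically important outcomes". Enrichment may then be used, "with the same objective of rejecting a meaningless rate of clinical activity". The paragraph sets no limit on the number of such subsets, no selection rule and no different threshold. It does not say whether the patients who suggested a subset are counted in it. Protocol 14.1 bases analyses on all treated patients.

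SAP 3.1.2 repeats the Stage 3A sample-size text, including the one-responder rule, but not this paragraph. SAP 3.8 says: "Exploratory subgroup analyses may be performed for descriptive purposes". SAP 3.7 applies no type I error control. SAP 1.1.3 states that the SAP will set out differences from the protocol's analytical objectives. SAP Section 5 lists several dropped analyses (MF subpopulations, Bayesian, correlative) but does not mention this objective.

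**The concern.** For the two named subsets, membership is known before any outcome, so zero responders is a possible result and the one-responder rule can fail. A subset identified afterwards has no such protection. If what draws attention to it is a patient who responded, and that patient stays in the count, a zero is impossible. Rejecting the no-responder result then only restates why the subset was picked.

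At stake is how the clinical study report may describe such a subset. Under the protocol wording it could be presented as having met the same standard as the prespecified subsets, with an observed response rate pushed up by the selection. Under SAP 3.8 it would be description only. Both standards are currently available to the report's authors.

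**Working it through.** **Inputs from the documents (Protocol 14.2.2).** Pass rule: at least 1 responder. Cohort: about 20. Prespecified subset: 8-10. Power case: 10 patients, true rate 0.15, 80%. True rates of 2% and 5% are assumptions, chosen to show how the rule behaves when activity is low.

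**1. The plan's own figure.** P(at least 1 responder) = 1 − (1 − p)^n. With n = 10 and p = 0.15: 1 − 0.85^10 = 0.803. The stated 80% reproduces.

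**2. One prespecified subset.**

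| True rate (assumed) | n = 8 | n = 10 |
|---|---|---|
| 2% | 0.149 | 0.183 |
| 5% | 0.337 | 0.401 |

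**3. A subset chosen because it holds a responder.** If X is the number of responders and the prompting patient is counted, P(X ≥ 1 | X ≥ 1) = 1 at any true rate above zero. The chance that such a subset can be found equals the chance of any responder in the cohort:

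- 2%: 1 − 0.98^20 = 0.332
- 5%: 1 − 0.95^20 = 0.642

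This treats all 20 patients as able to show the response type in question. For a response type limited to the 8-10 patients with the relevant baseline feature, the figure falls back to step 2.

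**4. If only new patients counted.** With 5 to 10 new patients at a 5% rate, the rule passes with probability 1 − 0.95^5 = 0.226 to 1 − 0.95^10 = 0.401. So the automatic pass comes from counting the prompting patient, not from retrospective identification alone.

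**5. Illustration of the inflated rate.** Assumptions: 20 patients; true rate 5%; 6 baseline features unrelated to response, each splitting the cohort exactly 10/10; the best of the 12 halves is chosen; at least one responder exists. By simulation, the selected half shows about 15% on average. The fair comparator is the whole cohort under the same condition: 0.05 / 0.642 = 7.8%. Selection therefore roughly doubles the apparent rate. The simplest case shows why: with 1 responder in 20 (5%), the half that contains the responder shows 1 in 10 (10%).

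**The case against.** The strongest reply has four parts.

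**The wording is looser than the concern.** A reader might infer that the protocol selects subsets by outcome, so that the rule always passes. The text does not say this. It does not require that a responder be seen first, and the shared objective can be read as attached to enrichment, that is, to enrolling more such patients. The no-responder definition and the demonstration rule are written for the two named subsets; retrospective ones are reached only through the shared objective. This stands as a limit: the automatic pass is conditional. But nothing in the protocol excludes the circular use.

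**The SAP already takes the safer position.** Protocol 14.5 leaves the details of efficacy analysis to the SAP, which omits the paragraph and keeps subgroups descriptive. A reader might call this a contradiction between the documents. It is better described as unreconciled: the SAP is narrower than a permissive protocol sentence but does not withdraw it.

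**The stage is exploratory and was curtailed.** After one responder, confidence intervals or power calculations may follow. SAP Section 5 says that Stage 3A enrollment was not continued and Stage 3B not started, and that descriptive analyses will follow. This stands and lowers the impact. It also makes a rule about counting only later-enrolled patients pointless. The optional interval would not cure the problem: for 1 of 10, the exact 95% interval is 0.3% to 44.5%, with no allowance for how the ten were chosen.

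**Larger numbers are not supported.** Pooling both cohorts would give 1 − 0.95^40 = 87%, but Protocol 14.2.2 evaluates each cohort individually. Setting the selected 15% against the true 5% would credit to subset selection an increase that partly comes from requiring at least one responder.

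**Conclusion.** The point holds in conditional form. Where a retrospective subset is chosen for containing a responder and that patient is counted, the one-responder rule cannot fail and carries no information; Protocol 14.2.2 permits this. In a 20-patient cohort the opportunity arises with probability 33% or 64% at assumed true rates of 2% or 5%, about twice or somewhat less than twice the 15-18% or 34-40% for one prespecified subset. Those figures assume that every patient in the cohort can show the response. The 15% against 7.8% comparison is an illustration that depends on the assumed six features, which are not in the documents.

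The documents do not show that the sponsor intends this use, that the SAP contradicts the protocol, or that any confirmatory decision now depends on it. The severity is low: a wording correction worth making before the report, because SAP Section 5 leaves the protocol objective in place.

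**What to change.** State in SAP Section 5 and SAP 3.8, and in Protocol 14.2.2 if it is amended for other reasons, that retrospectively identified subsets:

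- are descriptive only;
- cannot be used to reject a meaningless rate or to claim demonstrated activity;
- are reported together with the number of subsets examined.

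The cost is a sentence or two and no new data. The small downside is that responders who prompted a subset no longer count as evidence for it. Their responses still appear in the cohort results and in the descriptive subgroup tables.
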